10.3 Analysis Datasets

All participants will be included the analysis dataset. The analysis dataset will include all relevant variables:
Outcome variables

- Relative contribution (RC)
- Muscle contribution (MC)
- CST lesion load (CSTLL)

Independent variables

- Loading (via exoskeleton)

Demographic variables

- Age
- Height
- Weight
- Time since stroke (stroke only)
- Lesion type (hemorrhagic vs. ischemic)
- Arm length
- Handedness
- Fugl-Meyer score (stroke only)

10.4 Description of Statistical Methods

10.4.1 General Approach

This study is a repeated measures cohort design. Two groups of participants (stroke, healthy control) will perform a reaching task with and without an exoskeleton device. Primary endpoint measures will be compared within-subject to assess the effects of exoskeleton loading on coordination (kinematic: RC and muscular: MC). A between-subjects analysis will be performed to assess differences in arm control between stroke and healthy control participants.

- For descriptive statistics, we will use ranges, means, and standard deviation as appropriate. For example individual ages will be reported and further summarized with mean and standard deviation.
- For inferential statistics, we will perform two-tailed paired- and unpaired t-tests and ANOVA where appropriate. Statistical significance will be assessed at the Type-I error less than $p = 0.05$ level. See Section 10.4.2.
- Covariates will not be pre-specified
- Statistical test assumptions will be analyzed following data collection. Appropriate adjustments (e.g., normality) will be performed, such as transformation or the use of non-parametric tests.

10.4.2 Analysis of the Primary Efficacy Endpoint(s)

Primary study objective (change in RC, MC)

- Two-way ANOVAs on RC are conducted with within-subjects factor block (baseline, loading, retention) and between-subjects factor cohort (healthy, stroke). Three-way ANOVAs on MC are performed with within-subjects factors block and muscle (deltoid, biceps) and between-subjects factor cohort.

10.4.3 Analysis of the Secondary Endpoint(s)

Secondary study objective (Motor performance vs. CST lesion load)

- We first perform linear regressions to assess the relationship between lesion load and Upper Extremity Fugl-Meyer (UE-FM). Coefficient of determination (R^2) values ranging from 0.2 to 0.7 have been previously reported (Cassidy et al., 2018; Feng et al., 2015; Lin et al., 2019; Zhu et al., 2010).
- We regress lesion load into the change in RC (ΔRC), change in MC (ΔMC), and tradeoff slope. Any motor performance measures that fail to achieve R^2 values greater than 0.2 when regressed to CST lesion load will be discarded from further analysis.

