3.2 Secondary Objectives

To establish corticospinal tract lesion load as a correlate of kinematic and neuromuscular responsiveness to exoskeletal support. We do this by associating the change in RC (or MC) with the variance in overlap between the lesion and the corticospinal tract (CST lesion load) using clinical standard of care MRI scans.

4 Study Design and Endpoints

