4.2.2 Secondary Study Endpoints

The secondary endpoint will be a significant relationship between the change in MC (% decrease in MC) and CSTLL with an R^2 value greater than 0.4 (Brunfeldt et al., *in review*).

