10.2 Statistical Hypotheses

Primary endpoint. Exoskeletal support will increase RC in stroke participants. Paired t-test comparing RC from baseline to loading blocks.

Primary endpoint. Exoskeletal support will decrease MC in stroke participants. Paired t-test comparing MC from baseline to loading blocks.

Secondary endpoint. There will be an association between change in RC (or MC) and CST lesion load. Independent linear regressions (RC vs. CSTLL and MC vs. CSTLL).

Secondary endpoint. RC values in stroke participants will be less than RC values in healthy controls during baseline blocks (t-test). MC values in stroke participants will be greater than MC values in healthy controls during baseline blocks (t-test).

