10.5 Sample Size

Study Hypotheses: (Primary study objective)

- A power analysis using a moderate effect size (Cohen's $f = 0.25 - 0.3$) on MC, power of 0.8, and significance level of 0.05 suggests a total sample of 20-28 participants (10-14 per group). This is consistent with previous work using shared cursor tasks in stroke (Brunfeldt et al., 2022; Ranganathan et al., 2019).

Study Hypotheses: (Secondary study objective)

- An *a priori* power analysis with an effect size $f^2 = 0.7-0.9$, a power of $1-\beta = 0.8$ and error probability $\alpha = 0.05$ results in a target sample size of 12-14 participants. The estimated effect size was directly calculated from a Partial $R^2 = 0.4648$ using data from a feasibility study currently in preparation for publication. This R^2 value was taken from the relationship between lesion load and the change in MC from baseline to loading conditions.

Assumptions used in calculations:

- Assumed normal distribution, or corrected to normal distribution (e.g., via log-transform)
- We plan to enroll 30 participants, with between 6-8 stroke participants not meeting inclusion/exclusion criteria. The final $N = 12$ endpoint accounts for these dropouts.
- Data from withdrawn participants will not be included in the final dataset. Only those who complete all procedures will be included in the final analyses.

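### Dropping motor measures whose sample R² with lesion load is 0.2 or less selects on the estimate itself and inflates the R² of those kept

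*Combined protocol and SAP*

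**What the plan says.** Section 10.4.3 starts with a regression relating lesion load to UE-FM. It then regresses three motor measures on CST lesion load: change in RC, "change in MC (ΔMC), and tradeoff slope". The next sentence sets the rule: motor "measures that fail to achieve R^2 values greater than 0.2 when regressed to CST lesion load will be discarded from further analysis". The section ends there. No hold-out sample, cross-validation or shrinkage is described. The analysis that kept measures would enter is not specified, and nothing is said about reporting the measures that are dropped. Section 10.1 states that there will be no formal SAP, so no other document fills the gap.

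Other sections treat both associations as study questions in their own right. Section 3.2 says "We do this by associating the change in RC (or MC) with the variance in overlap between the lesion and the corticospinal tract", and section 10.2 lists "Independent linear regressions (RC vs. CSTLL and MC vs. CSTLL" as the analyses for that secondary hypothesis. Section 4.2.2 defines the secondary endpoint as "a significant relationship between the change in MC (% decrease in MC) and CSTLL with an R^2 value greater than 0.4". Section 10.5 bases the secondary sample size on a partial R² of 0.4648 for change in MC and arrives at 12 to 14 participants, with a final N of 12.

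**The concern.** A rule that keeps a measure only when its sample R² exceeds a cutoff, and then uses that same R², truncates the sampling distribution from below. What survives is too large on average, and in a sample of 12 the sampling spread is wide enough for this to matter.

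Two things are at stake. A measure with a real association can be set aside because of sampling error. And if only survivors are carried forward or reported, a reader who uses this pilot to plan later work sees a selected set of R² values; a study sized on them would be too small.

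Change in RC is the measure with least support behind it. It is named in sections 3.2 and 10.2, but the planning R² comes from change in MC only, the earlier lesion finding in section 2.2.1 concerns muscle activity, and the documents give no planning R² for RC.

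**Working it through.** **Inputs.** Cutoff R² > 0.2 (10.4.3). N = 12 stroke participants (Protocol Summary, 10.5), so residual df = 10. Planning R² = 0.4648 and α = 0.05 (10.5). Two-sided testing (10.4.1). True R² values of 0.20 and 0.30 are assumptions used to show the range; they are not planning figures from the documents.

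**1. Reproducing the plan's sample size.** f² = 0.4648/(1 − 0.4648) = 0.868. For a one-predictor regression F test with df 1 and N − 2 and noncentrality f²·N:
- f² = 0.7 needs N = 14 (power 0.82).
- f² = 0.868 needs N = 12 (power 0.83).
- f² = 0.9 needs N = 12 (power 0.84).

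The stated 12 to 14 reproduces.

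**2. Can the rule change a test or the endpoint?** The critical R² for two-sided p < 0.05 is t²/(t² + df) = 2.228²/(2.228² + 10) = 0.332. A measure with R² of 0.2 or less is therefore already non-significant and already below the 0.4 required by 4.2.2. The regressions are run before the rule applies. Type I error, power and the endpoint decision are unaffected.

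**3. What does R² = 0.2 mean at N = 12?**
- t = √(0.2 × 10/0.8) = 1.581, p = 0.145.
- r = √0.2 = 0.447, and Fisher z = 0.481.
- The 95% limits are 0.481 ± 1.96/√(12 − 3) = 0.481 ± 0.653 on the z scale, which gives r from −0.17 to 0.81.

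The upper limit corresponds to R² = 0.66. The planning value, r = √0.4648 = 0.68, lies inside the interval, and so does zero. A sample R² at the cutoff does not separate a weak association from the planned one.

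**4. Size of the selection bias, N = 12.** The bivariate normal columns come from simulation with 1,000,000 runs per row. The fixed-predictor columns use R² derived from noncentral F(1, 10) with noncentrality 12·R²/(1 − R²), which is the model behind the 0.83 power above.

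| True R² | Bivariate normal: discarded | Mean R², all → kept | Fixed predictor: discarded | Mean R², all → kept |
|---|---|---|---|---|
| 0.20 (assumed) | 47% | 0.249 → 0.397 | 43% | 0.265 → 0.397 |
| 0.30 (assumed) | 31% | 0.331 → 0.437 | 25% | 0.356 → 0.439 |
| 0.4648 (planning) | 12% | 0.474 → 0.522 | 6% | 0.511 → 0.534 |

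The increase due to the filter is the kept mean minus the all-sample mean:
- At 0.20: 0.148 (bivariate normal) and 0.132 (fixed predictor).
- At 0.30: 0.106 and 0.083.
- At 0.4648: 0.048 and 0.023.

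With no association at all, a measure passes the cutoff with probability 0.145. The mean R² is then 0.317 among kept samples against 0.091 over all samples.

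**The case against.** The strongest reply is that the harm rests on a practice the plan does not state. Dropping a measure from later analysis is not the same as leaving it out of the report. The RC and MC regressions are run first, are named in 3.2 and 10.2, and are not withdrawn anywhere. No later model is described and section 4.2.3 lists no exploratory endpoints, so the rule may have nothing to act on. This stands as a limit on the claim: the bias arises only if kept measures alone are carried forward or reported. It does not remove the concern, because the plan contains an explicit discard rule and no sentence that protects the discarded results.

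The effect is also small at the only planning value in the documents: 0.02 to 0.05, against a standard deviation of sample R² of about 0.21 there (bivariate normal simulation). That is correct. The planning value concerns change in MC alone, however; for change in RC and tradeoff slope the true R² is unknown, and the bias grows as it falls.

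Sample R² is biased upward at N = 12 even without the filter (0.249 on average when the truth is 0.20). That also stands. Removing the rule takes away the added part only, and the interval reported beside each estimate shows how imprecise it is.

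Finally, a prespecified triage threshold can be defended in a proof-of-concept pilot, and adding a reporting sentence would be enough without deleting the rule. Full reporting is indeed the essential part. But prespecification does not remove truncation bias, and a triage rule that feeds no defined analysis does no useful work.

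**Conclusion.** The concern holds, at moderate weight. The rule selects on the quantity being estimated, in the same 12 participants, with a cutoff that cannot distinguish no association from the planned one. If only kept measures are carried forward or reported, the filter raises mean R² by 0.02 to 0.05 at the planning value of 0.4648, and by 0.08 to 0.15 if the true R² lies between 0.20 and 0.30.

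These figures assume N = 12 and a linear model with normal errors; the ranges cover a random normal predictor and a fixed one. No hypothesis test, power figure or endpoint decision is affected. The loss is in unbiased estimation and in a complete answer to questions that the plan itself poses.

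**What to change.** Delete the discard sentence in 10.4.3 and put in its place: *Slope, R² and 95% CI will be reported for UE-FM, change in RC, change in MC and tradeoff slope against CST lesion load, whatever their size.* UE-FM is listed for completeness; the discard rule is not clearly aimed at it.

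Leave the endpoint in 4.2.2 and the hypotheses in 10.2 as they are. No new testing hierarchy is needed.

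The cost is one sentence and a slightly longer results table, with no extra data, participants or staff. The chance of meeting each criterion at the planning value stays the same: 0.83 (fixed predictor) or 0.74 (bivariate normal) for p < 0.05, and 0.73 or 0.65 for R² > 0.4.

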10.4.4 Safety Analyses

The study does not contain safety endpoints. Adverse events will be coded using the following identifying table:

If the report is supplied as a narrative, the minimum necessary information to be provided at the time of the initial report includes:

• Study identifier	• Current status
• Study Center	• Whether study treatment was discontinued
• Subject number	• The reason why the event is classified as serious
• A description of the event	• Investigator assessment of the association between the event and study treatment
• Date of onset	

10.4.5 Adherence and Retention Analyses

Adherence to the protocol will be assessed, calculated, and verified by the study investigator, [name]. [name] is under full control of the administration of the intervention. The intervention dose has been verified in previous work to be safe for participants (Brunfeldt et al., in review). In the event of a participant's wish to discontinue the protocol before study endpoint, that individual's data will be removed from analysis.

10.4.6 Baseline Descriptive Statistics

Participants will be selected from the MOBILIS lab registry. We will ensure that both groups (stroke vs. healthy control) will have the same number (frequency analysis) of men and women. We will also age match across groups. We may perform a t-test on age to ensure parity between groups.

10.4.7 Planned Interim Analysis

N/A. Single session study

10.4.7.1 Safety Review

Participants are free to withdraw from participation in the study at any time upon request. An investigator may terminate participation in the study if:

- Any clinical adverse event (AE) or other medical condition or situation occurs such that continued participation in the study would not be in the best interest of the participant
- The participant meets an exclusion criterion (either newly developed or not previously recognized) that precludes further study participation
- The participant fails to adhere to protocol requirements
- Subject withdraws consent
- Subject experiences excessive fatigue or discomfort

Abrupt withdrawal or termination from study will not affect participant safety or clinical management.

10.5 Sample Size

Study Hypotheses: (Primary study objective)

- A power analysis using a moderate effect size (Cohen's $f = 0.25 - 0.3$) on MC, power of 0.8, and significance level of 0.05 suggests a total sample of 20-28 participants (10-14 per group). This is consistent with previous work using shared cursor tasks in stroke (Brunfeldt et al., 2022; Ranganathan et al., 2019).

Study Hypotheses: (Secondary study objective)

- An *a priori* power analysis with an effect size $f^2 = 0.7-0.9$, a power of $1-\beta = 0.8$ and error probability $\alpha = 0.05$ results in a target sample size of 12-14 participants. The estimated effect size was directly calculated from a Partial $R^2 = 0.4648$ using data from a feasibility study currently in preparation for publication. This R^2 value was taken from the relationship between lesion load and the change in MC from baseline to loading conditions.

Assumptions used in calculations:

- Assumed normal distribution, or corrected to normal distribution (e.g., via log-transform)
- We plan to enroll 30 participants, with between 6-8 stroke participants not meeting inclusion/exclusion criteria. The final $N = 12$ endpoint accounts for these dropouts.
- Data from withdrawn participants will not be included in the final dataset. Only those who complete all procedures will be included in the final analyses.

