Finally, we will obtain neuroimaging data from the participant's electronic medical record (EMR). The Study Investigator will obtain written consent (see Consent Form) to access the participant's EMR, where they will download the diffusion weighted image (DWI) scan obtained through standard of care at NYULMC. **No new imaging will be required.** Downloaded DWI images will have personal identifying information removed. The DWI will be analyzed in the ITK-SNAP (<http://www.itksnap.org/pmwiki/pmwiki.php>). We use this software to manually trace the lesion to obtain a lesion mask. This lesion mask is then standardized to the Montreal Neurological Institute stereotaxic space (Mazziotta et al., 2001) using the SPM12 mapping software (Karl Friston, <https://www.fil.ion.ucl.ac.uk/spm/>). We then determine the overlap between the lesion mask and the CST (Zhu et al., 2010).

Study Timeline

The study will take place on the NYULMC campus in a single, 2-hour session.

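### Section 10.5 claims 80% power for the lesion-load regression, but at the final N of 12, with lesion load observed rather than set, power is about 0.67-0.76 for p < 0.05 and 0.56-0.66 for the full endpoint

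*Combined protocol and SAP*

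**What the plan says.** Section 10.5 (secondary study objective) gives an a priori power analysis with f² from 0.7 to 0.9, power 0.8 and alpha 0.05, which "results in a target sample size of 12-14 participants". The effect size is derived from a partial R² of 0.4648 between lesion load and the change in MC in a feasibility study. The assumptions listed below it set the final N at 12, and the Protocol Summary likewise plans 12 participants with stroke.

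The analysis in section 10.2 is "Independent linear regressions (RC vs. CSTLL and MC vs. CSTLL", under a hypothesis of association with no direction. Section 10.4.1 says "we will perform two-tailed paired- and unpaired t-tests and ANOVA where appropriate" and does not mention sidedness for regression.

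Section 4.1 describes how lesion load arises: the lesion is traced on a standard-of-care scan, normalised to a template, and "We then determine the overlap between the lesion mask and the CST". Section 5 recruits by convenience sampling, and no selection on lesion load is described. Section 4.2.2 defines the secondary endpoint as a significant relationship between change in MC and lesion load that also has R² above 0.4.

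**The concern.** The usual power formula for regression in terms of f² conditions on the predictor values. It acts as if the spread of lesion load in the 12 participants were known in advance and equal to the spread assumed in f². Here the spread is whatever the recruited participants happen to have. With 12 people it varies a good deal from sample to sample, and averaging over that variation lowers power. The planning effect is itself an R² observed in patients, so the power that matters for planning is the unconditional one.

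Two further points push the same way. The final N is the lower end of the plan's own 12-14 range. The power statement also covers significance only, while the declared endpoint adds a threshold on R².

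At stake is how the lesion-load result is read. Section 2.2.1 reports no significant group-level change in RC or MC in the preceding stroke study, but individual differences that lesion characteristics could explain. Lesion load is therefore a main lead carried into this study, and section 10.5 is the only place where its power is stated.

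**Working it through.** **Inputs.** From section 10.5: f² = 0.7 to 0.9, R² = 0.4648, power 0.8, alpha 0.05, final N = 12. From section 10.2: one predictor per regression. From section 4.2.2: R² > 0.4. Two-sided testing is taken as the natural reading, because the hypothesis has no direction and the other tests are two-tailed. Like the plan, the check uses the partial R² as the effect size for a one-predictor regression.

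**Step 1: effect sizes.** f² = R²/(1 − R²) = 0.4648/0.5352 = 0.868, inside the stated range. Conversely R² = f²/(1 + f²), so f² = 0.7 is R² = 0.412 and f² = 0.9 is R² = 0.474.

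**Step 2: reproduce the plan's figure.** For a fixed predictor, power = P[F′(1, N − 2; λ) > F(0.95; 1, N − 2)], where F′ is noncentral F and λ = f² × N.

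| f² | Power at N = 12 | Smallest N for 0.80 (power there) |
|---|---|---|
| 0.7 | 0.743 | 14 (0.819) |
| 0.868 | 0.828 | 12 (0.828) |
| 0.9 | 0.841 | 12 (0.841) |

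This gives 12-14 exactly. At f² = 0.7 the same method leaves N = 12 short of 0.80.

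**Step 3: random predictor.** If lesion load is normal, its sum of squares in the sample follows a chi-square distribution with N − 1 degrees of freedom, in units of its population variance. So λ becomes f² × χ²(N − 1), and the power in step 2 is averaged over that distribution.

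| f² | Power at N = 12 | Power at N = 14 | Smallest N for 0.80 |
|---|---|---|---|
| 0.7 | 0.666 | 0.747 | 16 |
| 0.868 | 0.744 | 0.819 | 14 |
| 0.9 | 0.756 | 0.830 | 14 |

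Simulation with 200,000 data sets per case gave 0.665, 0.743 and 0.758 at N = 12. Solving for the effect that gives 0.80 at N = 12 yields a population R² of about 0.51, above the plan's whole range of 0.412 to 0.474.

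**Step 4: the declared endpoint.** At N = 12 the critical F(1, 10) is 4.965, so p < 0.05 needs a sample R² above 4.965/(4.965 + 10) = 0.332. The 0.4 threshold is higher and therefore decides the endpoint. Random-predictor power for p < 0.05 and R² > 0.4 at N = 12 is 0.560 (f² = 0.7), 0.648 (f² = 0.868) and 0.662 (f² = 0.9). More participants barely help, because the assumed population R² lies close to the threshold: at N = 16 the figures are 0.557, 0.660 and 0.677.

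**The case against.** The stated range is correct for the method that the f² notation implies. Conditioning on the predictor is a common planning convention, and the regression test keeps its validity when the predictor is random. That stands: a reader might infer an arithmetic error, and there is none. The disagreement concerns which power model suits an observed predictor.

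A reader might also infer that 12-14 can arise only from a fixed-predictor calculation. The documents do not support this, because they name neither the predictor model nor the sidedness of the regression test. A one-sided Fisher z test of the correlation also gives 14 and 12. Two-sided remains the natural reading, but it is an inference.

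Nor does the predictor model explain the whole shortfall. At f² = 0.7 the fixed model already gives 0.743 at N = 12, so part of the 0.67 comes from taking the lower end of the plan's range. At R² = 0.4648 the model effect is 0.828 − 0.744 = 0.084, about 8 points. In participants the difference is two (14-16 against 12-14), which is small for a pilot.

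It is tempting to go further and assume skewed lesion load, or to shrink 0.4648 for small-sample bias. The documents give no distribution for lesion load. Section 10.5 assumes normality or a transformation towards it, without naming the variable. It also gives no sample size or covariates for the partial R². Neither extension can be supported from the documents.

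**Conclusion.** The point holds as a gap in the power statement. With 12 stroke participants, two-sided alpha 0.05 and lesion load as a random normal predictor, power for p < 0.05 is 0.74 at R² = 0.4648 and 0.67-0.76 over f² = 0.7-0.9. The fixed model gives 0.83 and 0.74-0.84. At the plan's own R², the chance of missing a true association is 26% rather than 17%. For the endpoint as declared, power is about 0.65 (0.56-0.66). The stated 0.8 is therefore not reached at N = 12 anywhere in the plan's effect range.

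The conclusion rests on three assumptions: a two-sided test, normally distributed lesion load, and the plan's partial R² serving as the one-predictor effect. The two-sided reading matters: a one-sided random-predictor calculation would need 13 at f² = 0.7 and 11 at f² = 0.9. A null lesion-load result should not be weighed against a claimed 80%. This is a matter of stating the precision of a secondary objective honestly; neither the design nor the planned regression is invalidated.

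**What to change.** Replace the secondary-objective power statement in section 10.5 with wording such as:

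> With 12 stroke participants, two-sided alpha 0.05 and lesion load treated as a random normal predictor, power for p < 0.05 is 0.74 at R² = 0.4648 (0.67-0.76 over f² = 0.7-0.9). Power for the full endpoint (p < 0.05 and R² > 0.4) is about 0.65 (0.56-0.66). A population R² of about 0.51 is required for 80% power for p < 0.05.

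This also puts on record the predictor model and the sidedness, which the plan now leaves open. If the investigators intended a one-sided test, they should say so and recalculate. The cost is a short edit and a less favourable power figure. No extra enrolment, visits or change of analysis is required.

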Title	A pilot proof of concept, single site study to assess the effect of exoskeletal support on motor control strategies in individuals with stroke
Short Title	Exoskeletal support in stroke
Brief Summary	This interventional study will measure motor performance, including 3D movement analysis and muscle activity, in response to exoskeleton assistance. The cohort design will compare stroke patients to healthy controls. Data collection will be conducted in a single, 2-hour session. We will also access stroke patients' brain MRIs that were obtained as standard of care during acute admission for stroke.
Phase	Pilot
Objectives	The primary objective is to examine in a VR environment whether additional gravity compensation from exoskeletal support will improve bimanual coordination in stroke patients. A second primary objective is to determine intervention effects on muscle control processes underlying bimanual coordination. As a secondary objective, we aim to correlate these measures with measures of stroke lesion characteristics.
Methodology	Cohort design
Endpoint	The primary endpoints will be a 2% increase in RC and a 5% decrease in MC. The secondary endpoint will be a significant relationship between the change in MC (% decrease in MC) and CSTLL with an R^2 value greater than 0.4
Study Duration	12 months
Participant Duration	One, 2-hour session
Duration of IP administration	Approximate 15 minutes
Population	24 participants; 12 with history of stroke more than 6-months prior to enrollment, 12 healthy age- and gender-matched controls. Males and females 18-years old and older from with and without diagnosis of stroke.
Study Site	Single-center (NYULMC)
Number of participants	24
Description of Study Agent/Procedure	We use a custom designed and built exoskeleton device that applies a torque to both shoulders. Torque values do not exceed 50% of the torque due to gravity. The device is mounted to a testing chair and attached to the participant using Velcro straps.
Reference Therapy	N/A
Key Procedures	No clinical procedures are required
Statistical Analysis	Inferential group statistics (t-test, mixed design ANOVA); correlation, linear regression

Schematic of Study Design

1 Key Roles

Principal Investigator

[name], Associate Professor
NYU Grossman School of Medicine
[name]
T [contact] (ACC)
[contact]

Study Investigator

[name], Postdoc
[name]
[contact]
[contact]

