4.2.3 Exploratory Endpoints

N/A

5 Recruitment

Starting immediately after IRB approval and lasting for approximately 12 months, subjects will be acquired by convenience sampling. The Study Investigator ([name]) will recruit subjects via a participant registry maintained by the Principal Investigator ([name]). The participant registry includes both survivors of stroke and healthy control participants. The registry is maintained by the PI to "develop a resource that researchers can use to recruit healthy individuals and patients with stroke in IRB-approved studies conducted by the Mobilis Laboratory" (s18-00959). We may also recruit participants through word of mouth from other studies conducted in the PI's laboratory.

The patient's affected hand will be examined to determine if the patient's impairment satisfies inclusion/exclusion criteria in one of the NYULMC treatment rooms allocated for research activities. After it is determined that the subject is eligible to participate in the study, the consent process will proceed. During the consenting process, all subjects will have the purpose of the experiment, the complete procedure, and any potential risks involved in participation in the study explained to them by the investigators. Participants in the stroke group will receive a one-time \$50 check following their participation in our study. Healthy control participants will receive a one-time \$25 check. The reason for this difference in value is the potential for increased burden on stroke patients regarding transportation (i.e., some are not medically cleared to operate a motor vehicle) and care due to their impairment.

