5.5 Total Number of Participants

Recruitment will end when approximately 24 participants are enrolled. It is expected that approximately 30 participants will be enrolled in order to produce 24 evaluable participants.

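### Section 10.5's final N of 12 stroke participants holds only at the low end of its own 6–8 loss range, and section 5.5 gives two incompatible recruitment totals

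*Combined protocol and SAP*

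**What the plan says.** The Protocol Summary sets the target population as "24 participants; 12 with history of stroke more than 6-months prior to enrollment, 12 healthy age- and gender-matched controls".

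The assumptions in section 10.5 (Sample Size) state "We plan to enroll 30 participants, with between 6-8 stroke participants not meeting inclusion/exclusion criteria", followed by "The final $N = 12$ endpoint accounts for these dropouts". They then add "Data from withdrawn participants will not be included in the final dataset", so that only completers are analysed. Section 10.4.5 says the same of anyone who discontinues. The stroke/control split of the 30 is not given anywhere.

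Section 5.5 has two consecutive sentences on the total: "Recruitment will end when approximately 24 participants are enrolled" and "It is expected that approximately 30 participants will be enrolled in order to produce 24 evaluable participants".

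On the order of events, section 5 (Recruitment) says "After it is determined that the subject is eligible to participate in the study, the consent process will proceed". Section 7.2 opens the session with consent, and section 7.2.2 lists consent before the check of inclusion and exclusion criteria.

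Section 5.6.2 foresees replacing withdrawn participants. For the procedure it cites a section 5.4 on recruitment and retention strategies, but section 5.4 is headed Duration of Study Participation.

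**The concern.** The evaluable stroke N carries the secondary objective (lesion load against change in MC or RC) and the within-stroke primary comparisons. A loss range whose middle and upper values do not give the N said to account for it leaves that N unsecured.

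Three further gaps add to this:

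- The allowance is for eligibility failures, although the next sentence calls them dropouts. Nothing in the 30 is set aside for people who start and withdraw, and they are removed from the analysis.
- The point at which recruitment ends is given as both about 24 and about 30 enrolled. Staff cannot tell whether 24 counts enrolled or evaluable people.
- Enrolment is not defined. Under the order in section 5, people who fail the criteria would never be enrolled. Section 10.5 counts them among the 30.

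**Working it through.** **Inputs.** Planned enrolment 30, losses L of 6 to 8 (all stroke) and final N = 12 come from section 10.5. The target of 12 stroke and 12 controls comes from the Protocol Summary. For the secondary objective, section 10.5 gives f² = 0.7–0.9, partial R² = 0.4648, alpha 0.05, power 0.8 and a target of 12–14. Its primary target is 20–28 in total, 10–14 per group. Two assumptions are mine: the final N of 12 means stroke participants, and 12 of the 30 are controls, so 30 − 12 = 18 are stroke.

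**Headcount.** Evaluable total = 30 − L; evaluable stroke = 18 − L.

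| Losses L | Total | Stroke | Controls |
|---|---|---|---|
| 6 | 24 | 12 | 12 |
| 7 | 23 | 11 | 12 |
| 8 | 22 | 10 | 12 |

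The plan's figure is reproduced exactly at L = 6. This is also the loss implied by section 5.5's second sentence (30 − 24 = 6, or 20%). It is not reproduced at 7 or 8.

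**Does another split rescue it?** With s stroke participants among the 30, 12 + 12 evaluable needs s − L ≥ 12 and 30 − s ≥ 12. That means s ≥ 12 + L and s ≤ 18, which is possible only if L ≤ 6. For example, 20 stroke and 10 controls with 8 losses keeps 12 stroke but has only 10 controls; 15 and 15 leaves 7–9 stroke. Covering 8 losses takes 12 + 8 = 20 stroke plus 12 controls, or 32.

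**Secondary power.** The model is a regression with one predictor, tested by a noncentral F with 1 and N − 2 degrees of freedom, λ = f² × N and two-sided alpha 0.05. The protocol's effect size reproduces: f² = 0.4648 / (1 − 0.4648) = 0.868. At N = 12, λ runs from 0.7 × 12 = 8.4 to 0.9 × 12 = 10.8. At N = 10 it runs from 7.0 to 9.0.

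| Stroke N | f² = 0.7 | f² = 0.868 | f² = 0.9 |
|---|---|---|---|
| 14 | 0.819 | 0.892 | 0.902 |
| 13 | 0.784 | 0.863 | 0.875 |
| 12 | 0.743 | 0.828 | 0.841 |
| 11 | 0.696 | 0.785 | 0.799 |
| 10 | 0.641 | 0.733 | 0.748 |

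The smallest N reaching 0.8 is 14 at f² = 0.7 and 12 at 0.868 and 0.9, so the stated 12–14 is reproduced. At N = 10 or 11, power is below 0.8 over the whole stated range, though at N = 11 and f² = 0.9 only by 0.001. Going from 12 to 10 costs 0.743 − 0.641 = 0.102, 0.828 − 0.733 = 0.095 and 0.841 − 0.748 = 0.093 at the three effect sizes.

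**Primary objective.** Ten stroke participants are still inside the stated 10–14 per group, at the f = 0.3 end. As a check, I took a group-by-block interaction with three blocks and equal groups, assuming a correlation of 0.5 between blocks. This reproduces 28 in total at f = 0.25 and 20 at f = 0.3. At a total of 22, power is 0.697 and 0.853 respectively, against 0.740 and 0.886 at 24.

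**The case against.** The best defence is that the plan works on its own terms. Thirty enrolled less 6 is 24, or 12 and 12, and the second sentence of section 5.5 says the same. Both sentences there are approximate, withdrawals can be replaced, and at worst the stroke group is two people short in a single-session pilot.

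Much of this stands. It is not correct to say that the numbers cannot deliver 12; they do so at 6 losses. The primary target is not missed at 10 per group. Part of the secondary shortfall also exists with all 12 in hand, since at f² = 0.7 power is 0.743 even then. That part is not due to enrolment.

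What does not stand is the statement that N = 12 accounts for the whole 6–8 range. The word approximately does not turn 24 into 30. Replacement is foreseen, but its procedure points to a section that does not contain it, and it cannot be squared with a stop at 24 enrolled.

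A reader might also take the 24-enrolled stop as 12 stroke and 12 controls, subtract 6–8, and infer that only 4–6 stroke participants would remain. The documents do not support that. Section 10.5 ties the 6–8 losses to 30 enrolled, and the next sentence of section 5.5 sets 24 as the evaluable number. If eligibility is settled before enrolment, as section 5 has it, the failures would not come out of the 24 at all.

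**Conclusion.** The point holds in limited form. Over the protocol's own loss range the evaluable stroke N is 10–12, not 12, before any withdrawals. This assumes 12 controls among the 30; the total of 22 at 8 losses needs no such assumption. The consequence falls on the secondary objective: about 9 to 10 points of power between N = 12 and N = 10, with the stated 0.8 missed at 10 or 11 for every effect size in the stated range. The primary target is met only at its lower end.

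The contradiction within section 5.5, and between its first sentence and section 10.5, rests on no assumption. Neither does the conflict over whether eligibility or consent comes first. These passages should be corrected before the sample-size statement is relied on, but they are not a reason to think the study cannot reach its target.

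**What to change.** - **Section 5.5:** replace both sentences with one rule. Recruitment ends when 12 stroke participants and 12 matched controls are evaluable, meaning eligible and all procedures completed, with usable DWI for the stroke group.
- **Section 10.5:** state the stroke/control split. Then either give a consented total that covers the stated range (20 stroke + 12 controls = 32 for 8 losses), or keep 30 and restate the evaluable stroke N as 10–12, with power of 0.64–0.75 at 10 and 0.74–0.84 at 12.
- **Losses:** separate eligibility failures from withdrawals. The 32 covers only the former, so either add an allowance or state that withdrawals are replaced until the evaluable count is reached. Correct the cross-reference in section 5.6.2.
- **Enrolment:** define the term, and reconcile section 5 (eligibility before consent) with sections 7.2 and 7.2.2 (consent first).

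The cost is wording in these sections, plus at most about two more consents than the planned 30 if 8 stroke participants fail eligibility, or a slightly less favourable stated N. Any allowance for withdrawals would be extra.
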